18.2. Statistical analysis

18.2.1. Analysis of main endpoint

The primary endpoint is the ORR i.e. the proportion of nivolumab treated patients achieving a response (PMR and CMR compared to end of first or second line salvage treatment scan; PET0) after either 4 (PET4) or 8 cycles (PET8). This will be presented as a proportion with 80% confidence intervals.

Any patient without a response scan will be counted as a non-response for the primary analysis (i.e. the denominator will be all eligible nivolumab treated patients). However, a secondary analysis may also be conducted excluding any patient who drops out before the first response scan for reasons other than disease progression or death from disease.

Analysis of the primary endpoint will take place after all patients have finished nivolumab treatment and response data is available.

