3.2. Trial Endpoints

Primary endpoints

• Overall response rate (ORR) by PET-CT scan following 4-8 cycles of nivolumab

Secondary endpoints

- Progression-free survival (PFS) at 1 year
- Overall survival (OS) at 1 year
- Proportion of patients proceeding to SCT (ASCT or alloSCT)
- Safety & toxicity of nivolumab, particularly autoimmune toxicity
- OS and PFS stratified by partial metabolic response (PMR) versus complete metabolic response (CMR) on FDG-PET
- Transplant-related mortality and rate of serious complications of allogeneic transplant (grade 3-4 graft-vs-host disease, hyperacute graft-vs-host disease and steroid-responsive febrile syndrome)

Exploratory endpoints

- Correlate PET positive disease with histological evidence of disease on biopsy to establish biopsy negative PMR rate (subject to patient consent)
- Correlate disease response, as assessed by FDG-PET and histology, with serological markers, including serum TARC
- Evaluate the correlation between response to nivolumab and biological parameters e.g. PD-1 expression on Reed-Sternberg cells

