8.8. Contraindications

According to the IB for nivolumab, no drugs are contraindicated during nivolumab treatment.

Form

Form

Form

Form

Any other systemic anti-cancer therapy or radiotherapy is prohibited while the patient is receiving trial treatment. Steroids should be weaned down to ≤10mg/day (prednisolone; or the equivalent dose of other steroids) within 7 days prior to starting trial treatment.

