9.5. Assessments on Completion of Trial Treatment

For patients who withdraw from trial treatment for any reason during cycles 1-3 of nivolumab:

• Lung function test (to be performed as soon as possible after decision to stop trial treatment, and before the next line of treatment begins)

For patients in CMR (Deauville 1-3) or with progressive disease after 4 cycles of nivolumab

 Lung function test (to be performed as soon as possible after receiving the PET-CT central review result)

If a biopsy is performed to confirm progressive disease, please send the block to HMDS, Leeds (see section 10).

For patients who withdraw from trial treatment for any reason during cycles 5-7:

- PET-CT scan to be carried out at least 11-13 days after last trial treatment administration, as per trial requirements on an approved scanner, and images sent to the PET core lab for central review (see trial Imaging Manual for details).
- Lung function test (to be performed as soon as possible after decision to stop trial treatment, and before the next line of treatment begins)

For patients who complete all 8 cycles of trial treatment:

- PET-CT scan to be carried out on cycle 8, day 11-13 as per trial requirements on an approved scanner, and images sent to the PET core lab for central review (PET8; see trial Imaging Manual for details).
- Contrast enhanced CT scan (ceCT). If feasible, this should be performed at the same imaging session as the PET-CT. If performed at the same session, the ceCT scan should be performed after the low dose PET-CT (see trial Imaging Manual for details).
- Repeat lymph node biopsy (if patient is PET positive and has consented for a repeat biopsy). Block to be sent to central laboratory (HMDS) (see section 10.1 and Laboratory Manual for details)
- Lung function test (to be completed 10 days after last nivolumab administration ±2 days)

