- 10 9- Biopsy to be performed at relapse if clinically indicated. Block to be sent to HMDS.

Investigations during treatment

Investigations to be performed within 3 days prior to the start of the cycle unless otherwise stated.

	Beginning of Cycle 1	Beginning of Cycle 2	Beginning of Cycle 3	Beginning of Cycle 4	Cycle 4 day 11-13	Beginning of Cycle 5	Beginning of Cycle 6	Beginning of Cycle 7	Beginning of Cycle 8	Cycle 8 day 11-13
Clinical examination	Х	Х	Χ	Χ		Χ	Χ	Х	X	
Full blood count with differential	Х	Х	Χ	Х		Х	Х	Х	Х	
Biochemistry ¹	X	X	Χ	Х		Χ	Χ	Х	Χ	
Tests for autoimmune conditions ²	Х	Х	Х	Х		Х	Х	Х	Х	
Oxygen saturation	X ³	X ³	X ³	X ³		X ³	X ³	X ³	X ³	
Adverse event assessment	Х	Х	Х	Х		Х	Χ	Х	Х	
Thyroid function tests ⁴	X			Χ				Х		
Pregnancy test (WOCBP only)	X ⁵		Х			Х		Х		
Blood samples for translational research ⁶	Х	Х		Х			Χ		Х	
PET-CT scan (for central review)					Х		7	7	7	Х

Notes:

^{1 =} to include ALT/AST, total bilirubin, alkaline phosphatase, lactate dehydrogenase, urea, creatinine, calcium, albumin, magnesium, sodium, potassium, urate, glucose

^{2 =} Amylase, lipase, ACTH

^{3 =} Immediately prior to administration of nivolumab

^{4 = (}TSH & Free T4; Free T3 to be performed if TSH/Free T4 abnormal)

^{5 =} Pregnancy test must be performed within 24 hours prior to starting nivolumab

^{6 =} See section 10.2. To be sent to Weatherall Institute of Molecular Medicine, Oxford

^{7 =} If patient stops treatment during cycles 5-7, a PET-CT scan should be performed and sent for central review. This should be undertaken at least 11-13 days after last trial treatment administration.

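### The primary endpoint is defined inconsistently: section 18.2.1 leaves out the centrally reviewed scan required of patients who stop in cycles 5-7, which sections 1.1 and 3.2 and Appendix 3 would count

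*Protocol*

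**What the plan says.** The endpoint list in section 3.2, repeated in the summary in 1.1, gives the primary endpoint as "Overall response rate (ORR) by PET-CT scan following 4-8 cycles of nivolumab". Section 18.2.1 gives the analysis definition: the proportion of nivolumab-treated patients with PMR or CMR relative to PET0 "after either 4 (PET4) or 8 cycles (PET8"). Appendix 3 adds that patients with an indeterminate response (IR) are not counted in the ORR unless they later reach CMR or PMR as their best overall response.

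Section 9.5 schedules PET8 on cycle 8, day 11-13, for patients who complete all eight cycles. A separate list, headed "For patients who withdraw from trial treatment for any reason during cycles 5-7", requires a "PET-CT scan to be carried out at least 11-13 days after last trial treatment administration", with images sent for central review. Note 7 to the treatment table in Appendix 2.1 repeats this: "If patient stops treatment during cycles 5-7, a PET-CT scan should be performed and sent for central review". The lung function test in that same list in 9.5 is "to be performed as soon as possible after decision to stop trial treatment, and before the next line of treatment begins". The PET-CT carries no such condition.

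**The concern.** A patient who stops after five, six or seven cycles has had between 4 and 8 cycles and has a centrally read scan, but that scan is neither PET4 nor PET8. If PET4 showed no metabolic response (NMR) or IR, and the scan after stopping shows PMR or CMR, the patient is a responder under 3.2 (and, for IR, under Appendix 3) and a non-responder under 18.2.1. The rule in 18.2.1 for patients without a response scan does not settle this, because the patient does have PET4. The trial is judged on one count out of 30, so that count should not depend on which section is read.

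A second question arises only if the scan is counted. Its timing has a lower bound and no upper one, and it need not come before the next treatment. A scan taken after new treatment has begun could then be scored as a response to nivolumab.

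**Working it through.** **1. The plan's own figure.** Inputs from section 18.1: rate to rule out 0.40, expected rate 0.60, one-sided alpha 0.10, power 80%, n = 30, at least 16 responses. With exact binomial tails:

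- P(X ≥ 16 | 30, 0.40) = 0.0971, which is at most 0.10
- P(X ≥ 16 | 30, 0.60) = 0.8246, which is at least 0.80

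The design reproduces. With the threshold at 15, alpha would be 0.1754. With the threshold at 17, power would be 0.7145.

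**2. Who can be classified differently.**

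| Result at PET4 | What follows | Effect of the cycles 5-7 scan on ORR |
|---|---|---|
| CMR | stops after cycle 4 | none; already a responder |
| Progressive disease | stops after cycle 4 | none; no such scan |
| PMR | may continue | none; already a responder (only the CMR/PMR split can change) |
| NMR or IR | may continue | changes ORR if the patient stops in cycles 5-7 and the scan shows PMR or CMR |

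Only the last row matters, and only for patients who meet all of its conditions.

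**3. Size.** The protocol gives no number for that group. Assume k = 1, 2 or 3 of 30. The shift in ORR is k/30, which is 3.3, 6.7 or 10.0 percentage points.

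**4. Near the threshold.** Exact (Clopper-Pearson) 80% limits for x of 30 are the 0.10 quantile of Beta(x, 31 − x) and the 0.90 quantile of Beta(x + 1, 30 − x):

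- 15/30 = 50.0%: 37.0% to 63.0%, so 40% is not ruled out
- 16/30 = 53.3%: 40.1% to 66.2%, so 40% is ruled out

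One extra response changes the conclusion only when the count without it is exactly 15. If the rate on that narrower count is 0.40, P(X = 15) = 0.1754 − 0.0971 = 0.0783. If it is 0.60, P(X = 15) = 0.9029 − 0.8246 = 0.0783.

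**5. Effect on the operating characteristics under each reading.** The expected number of responders is 30 × 0.60 = 18 at the target rate and 30 × 0.40 = 12 at the rate to be ruled out.

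| k (assumed) | Scan not counted: rate (18 − k)/30 | P(X ≥ 16) | Scan counted, k responses due to later treatment: rate (12 + k)/30 | P(X ≥ 16) |
|---|---|---|---|---|
| 0 | 60.0% | 82.5% | 40.0% | 9.7% |
| 1 | 56.7% | 71.1% | 43.3% | 17.8% |
| 2 | 53.3% | 57.4% | 46.7% | 29.1% |
| 3 | 50.0% | 42.8% | 50.0% | 42.8% |

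The two halves belong to alternative readings and cannot be added. They show what k would do, not what k is likely to be.

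**The case against.** The best defence is that 4 to 8 cycles is simply how the protocol describes the regimen (2.1, 8.2, 8.3), that 1.1 and 3.2 use it as a headline, and that 18.2.1 is the operative definition. Appendix 3 also ties its criteria for progression and IR to PET4 or PET8, and the cycles 5-7 list omits the contrast-enhanced CT that accompanies those two scans. Leaving the scan out would also err on the conservative side. How an off-schedule scan is handled can properly be left to a statistical analysis plan, which is not shown.

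This carries some weight: 18.2.1 may have been meant as written. But the protocol never says so, it requires and centrally reads the scan, and Appendix 3 counts later conversion from IR. An analysis plan could settle the counting. It could not repair the timing of scans already done.

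On timing, the markers for note 7 sit, as printed, under the starts of cycles 6, 7 and 8, about 14 days after the last dose, and the wording echoes the day 11-13 timing of PET4 and PET8. A scan at about that time was probably intended, and the Imaging Manual, which is not available, may say so. The protocol text nevertheless sets only a minimum, and nothing in it directs sites to scan after new treatment.

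A reader might also infer from section 8.8, "Any other systemic anti-cancer therapy or radiotherapy is prohibited while the patient is receiving trial treatment", that chemotherapy or radiotherapy between PET0 and the first dose could be credited to nivolumab. The documents do not support pressing this. No sentence expressly bars it, but the note to item 5 of section 6.2.4 names only corticosteroids as usable after a positive PET-CT, and 8.2 limits the interval to 4 weeks. It forms no part of this point.

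**Conclusion.** The inconsistency is real and lies in the primary endpoint itself: the same patient can be a responder under 1.1, 3.2 or Appendix 3 and a non-responder under 18.2.1. The group is narrow, namely patients with NMR or IR at PET4 who stop in cycles 5-7 and then respond. Its size is not in the documents. The shift of 3.3 to 10 points assumes 1 to 3 such patients, all of them responding on that scan, and it alters the conclusion only if the count falls near 16 of 30.

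A reader might infer that the trial both loses true responses and gains false ones through this scan. That does not follow. If 18.2.1 governs, the scan is not counted and its late timing cannot inflate the ORR. If 3.2 governs, the scan is not lost, and the open timing becomes the issue. The point should be corrected. It does not undermine the design, whose sample size and threshold are sound.

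**What to change.** In 18.2.1, define response as CMR or PMR relative to PET0 on PET4, on PET8, or on the centrally reviewed scan of patients who stop in cycles 5-7, and state that only scans done before any new anti-lymphoma treatment count. Align 1.1, 3.2 and Appendix 3 with that sentence.

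In 9.5 and in note 7 of Appendix 2.1, give this PET-CT a latest time, to be set by the sponsor, and attach the condition that the lung function test already carries about preceding the next treatment. This governs which scan counts; it is not a rule about when further treatment may start.

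The cost is a wording amendment with the usual approvals. No scan is added, and the 30 patients and threshold of 16 stand. The small downside is that an occasional late scan will no longer count.

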18.2.2. Analysis of secondary endpoints and secondary analyses

Survival endpoints:

Progression free survival (PFS)

PFS time will be measured from the date of the PET scan after first or second line salvage treatment (PET0) until the date of progression or death (whichever comes first). Patients who are alive and progression free will be censored at the date last seen.

Overall survival (OS)

OS time will be measured from the date of the PET scan after first or second line salvage treatment (PET0) until the date of death. Patients who are alive will be censored at the date last seen.

Analysis of PFS and OS will take place once we have 1 year follow-up for all patients. Kaplan Meier survival analyses will be used for both.

Subgroup analyses will be performed for responders and non-responders i.e. do patients with a PMR do worse than those with a CMR after nivolumab treatment. Kaplan Meier survival analysis and Cox regression may be used, although this will be dependent on the numbers of patients with a response and the numbers of events.

PFS and OS will also be analysed by further treatment i.e. did the patient go on to have an allograft or autograft, though we acknowledge that numbers will be very small so analyses will be descriptive.

CMR/PMR rates

Proportions of patients achieving CMR and PMR will also be presented.

Adverse events:

Analysis will focus on grade 3/4 adverse events. The worst grade seen per patient will be shown for each event type.

AESIs will be reported in more detail, with autoimmune events of any grade presented. All analysis will be descriptive.

Transplant related mortality and the rate of serious complications of allo SCT will presented, though again, it is likely only descriptive statistics will be used.

Other analyses:

The association between pre-nivolumab biological parameters and response to nivolumab will be investigated. As numbers will be very small mostly descriptive statistics will be used i.e. numbers and percentages will be presented for binary/categorical data and means and medians (with ranges) for continuous measurements.

We will also look at changes in TARC levels in responders and non-responders.

PET negative patients not treated with nivolumab

We will look at PFS, OS and subsequent treatments for patients who are PET negative following first or second line salvage treatment (i.e. at PET0).

We will also look at whether there are baseline characteristics at diagnosis or relapse which are associated with response to initial salvage treatment. These will include extranodal disease (relapse), haemoglobin levels (relapse), duration of first remission (patients in first relapse only), initial treatment, location of relapse (within RT field or not) and stage (at diagnosis and relapse).

Interim analyses

There are no formal interim analyses or formal stopping rules, but an Independent Data Monitoring Committee (IDMC) will review all trial data yearly and can suggest stopping the trial if they have any concerns about safety or efficacy. Trial Management Group (TMG) meetings will be held approximately every 3-6 months and the committee will review safety data including full SAE listings.

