9.6. Assessments During Follow Up

Patients will be followed up for a minimum of 3 years. All efforts should be made by the Site to contact the patient's GP to assess their condition, if a patient fails to attend a clinic or cannot be followed up at site.

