9.6.2. Patients who receive nivolumab

Follow up in year 1 post treatment

Patients will be seen approximately once a month for the first 3 months, and every 3 months thereafter.

The following tests will be performed **1 month**, **2 months and 3 months** post treatment (30, 60 & 90 days after the last dose of Nivolumab respectively (±3 days)):

- Clinical examination
- Full blood count with differential
- Biochemistry (ALT/AST, total bilirubin, alkaline phosphatase, urea, creatinine, calcium, magnesium, sodium, potassium, LDH, albumin, urate, glucose)

- Tests for autoimmune conditions (amylase, lipase, ACTH)
- Thyroid function tests (TSH & Free T4; Free T3 to be performed if TSH/Free T4 abnormal)
- Adverse event assessment
- Pregnancy test (urine or serum; WOCBP only)
- Remission status assessment (investigations as per local policy) 3 month timepoint only

Blood samples for translational research

Blood samples are to be taken and sent to the central laboratory at the Weatherall Institute
of Molecular Medicine, Oxford at the 1 month post-treatment visit (30 days post last dose
of nivolumab (±3 days); see section 10.2 and Laboratory Manual for more details)

The following tests will be performed at months 6, 9 and 12 post treatment:

- Clinical examination
- Full blood count with differential
- Biochemistry (U&E, LFTs)
- Remission status assessment (investigations as per local policy)
- Assessment for late toxicity of nivolumab

In addition, at month 12 post treatment, the following test will be carried out:

Lung function test

Follow up from year 2 post treatment onwards

Patients will be seen annually. The following investigations will be performed:

- Remission status assessment (investigations as per local protocols)
- Assessment for late toxicity of nivolumab

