15.3. Losses to Follow-Up

See section 15.4 (Transfer of Care) for details of actions needed when a patient relocates or their care is transferred.

If a patient is lost to follow-up at a site every effort should be made to contact the patient's GP to obtain information on the patient's status.

Patients lost to follow up may be tracked by UCL CTC via registries such as the National Cancer Registration and Analysis Service, or the Health & Social Care Information Centre NHS Digital (England), NHS Wales Informatics Service (Wales) or the Information Services Division (Scotland).

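### PFS is censored at the date last seen, as OS is, so contact after the last disease check can count as progression-free time and can raise 1-year PFS if assessments are missed

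*Protocol*

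**What the plan says.** Section 3.2 lists "Progression-free survival (PFS) at 1 year" as a secondary endpoint. Under section 18.2.2, PFS runs from PET0 "until the date of progression or death (whichever comes first"), and for everyone else "Patients who are alive and progression free will be censored at the date last seen". OS is censored at the same date. Both use Kaplan-Meier, and "Analysis of PFS and OS will take place once we have 1 year follow-up for all patients".

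The follow-up sections show where disease is checked.

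- **Nivolumab patients (9.6.2).** Months 1, 2 and 3 share one list of tests, but the remission item reads "Remission status assessment (investigations as per local policy) 3 month timepoint only". The next list opens "The following tests will be performed at months 6, 9 and 12 post treatment" and includes a remission status assessment, as do the annual visits.
- **Patients not given nivolumab (9.6.1).** Every scheduled visit has a remission status assessment.
- **During treatment (9.4, 9.5).** Visits are two-weekly. Response imaging falls at PET4, at PET8, or after stopping in cycles 5-7.
- **Non-attenders (9.6).** "All efforts should be made by the Site to contact the patient's GP to assess their condition".
- **Lost patients (15.3).** "Patients lost to follow up may be tracked by UCL CTC via registries".
- **Loss of capacity after treatment (15.5).** Only survival follow-up continues.
- **Care at a non-trial site (12.2).** The trial site depends on updates sent to it.

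**The concern.** The date last seen suits OS, because seeing a patient establishes that the patient is alive. PFS also needs evidence that the disease has not progressed. Under the stated rule, a patient whose last remission assessment was at six months but who is known to be alive at thirteen can stay in the PFS risk set for the whole first year. Any progression in that interval that nobody looked for is counted as progression-free time.

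The error goes one way: it can raise PFS but not lower it. There is no control arm to share it, and with about 30 treated patients a few such cases move the estimate. The same rule feeds the PFS comparison of partial with complete metabolic responders and the description of PFS by later transplant. This is a rule the protocol fixes, not a detail it leaves open, so an analysis plan written from it would inherit the date.

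**Working it through.** **The plan's own figures.** The protocol gives no expected PFS rate, PFS threshold or dropout rate, so there is no PFS figure to reproduce. Its only powered figure is the response-rate design in section 18.1: 30 patients, at least 16 responses, 40% against 60%. Exact binomial tails give one-sided alpha 0.0971 and power 0.8246, and 30 is the smallest n that meets both limits. The PFS rule does not enter this calculation.

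**Hand check of the mechanism (assumed data).** Take 30 patients with 12 progressions spread evenly over months 1 to 11.5, six of them before month 6.5. The other 18 are seen after month 12.

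- Stated rule: nobody is censored before 12 months, so 1-year PFS = 18/30 = 60.0%.
- Let k of the 18 have their last assessment at 6.5 months. After six events, S = 24/30 = 0.800. Censoring k patients there leaves 24 − k at risk for the remaining six events, so S(12) = 0.800 × (18 − k)/(24 − k).
- k = 3: 0.800 × 15/21 = 57.1%, so the stated rule is 2.9 points higher.
- k = 5: 0.800 × 13/19 = 54.7%, so the stated rule is 5.3 points higher.
- Standard error at 60%: √(0.6 × 0.4/30) = 8.9 points.

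If all k patients had in fact progressed unseen, PFS would be 15/30 = 50.0% or 13/30 = 43.3%. That is a worst case, and neither censoring rule recovers it.

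**Simulation on the protocol's schedule.** Each setting has 30 patients and 4,000 runs, with Kaplan-Meier PFS read at 52 weeks. The following are assumptions, not protocol figures: exponential progression with true 1-year PFS of 50% or 70%; nivolumab starting 1-4 weeks after PET0; half the patients having 8 cycles; none or half of progressions found early through symptoms. In the contact-without-checks settings, a share of patients stop disease checks at a random time between weeks 8 and 52 but remain in contact. The entries are PFS under date-last-seen censoring minus PFS under last-assessment censoring, in percentage points.

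| Setting | True PFS 50% | True PFS 70% |
|---|---|---|
| Schedule followed, no dropout | 0.0 | 0.0 |
| Complete dropout, 10% per year | 0.1 | 0.1 |
| Complete dropout, 20% per year | 0.2 | 0.1-0.2 |
| 10% in contact without checks | 2.2-2.3 | 1.4 |
| 20% in contact without checks | 4.5-4.6 | 2.9 |
| 30% in contact without checks | 6.9-7.0 | 4.5 |

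Ranges cover the two symptom assumptions. The difference was never negative. It is near zero under complete dropout because contact and checks then end almost together, so nearly the same patients are at risk when progressions are recorded.

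**The case against.** The strongest reply is that the schedule already does most of the work. Every scheduled visit from month 3 after treatment, and every scheduled visit of patients not given nivolumab, includes a remission assessment. For anyone followed to plan beyond month 3, the last visit and the last assessment are normally the same date. The month 1 and 2 visits are not blind either: they include examination, blood count and biochemistry, and for patients who finish treatment they come soon after a centrally reviewed scan. Suspected progression triggers investigation (9.7), and confirmed progression is reportable at any time (12.5.2). This stands. It is why the effect is close to nil on schedule and why the month 1-2 visits contribute little.

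It can also be said that the protocol generally uses being seen to mean a visit, and that the rule requires the patient to be progression-free, which a registry record of vital status cannot show. That stands for registries: a reader might infer that registry tracing alone extends PFS, and the text does not support it. It does not settle GP contact, care elsewhere or survival-only follow-up. The OS sentence uses the same words, and no definition separates the two uses.

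Finally, PFS is secondary and has no decision threshold, and the assumed shares of 10% to 30% appear nowhere in the protocol. Both points are true. They limit the weight of the finding but do not make the date right for PFS.

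**Conclusion.** The concern holds in conditional form. The censoring sentence can credit unassessed time as progression-free, and any resulting bias in 1-year PFS is upward. The excess is 0.0 to 0.2 points if the schedule is followed, and about 1.4 to 7 points if 10% to 30% of patients remain in contact without checks. Those shares, the true PFS values and the timing inputs are assumptions. Even the largest excess is below one standard error of the estimate, but it is systematic and avoidable.

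Two stronger readings are not supported. A reader might infer that 1-year PFS is biased upward as planned; with assessments at every visit from month 3, that depends on missed checks followed by continued contact. A reader might also infer that the cohort that is PET-negative at PET0 is affected in the same way; its scheduled visits all include an assessment, so it is exposed only through off-schedule contact. The primary response-rate analysis, the 30 patients and the cut-off of 16 are untouched. The change is worth making before the data are seen, but it is not critical.

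**What to change.** Replace the PFS censoring sentence in section 18.2.2 with:

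*Patients alive without progression are censored at the date of the last assessment at which they were documented progression-free (PET0, PET4, PET8, the PET after stopping in cycles 5-7, or a follow-up remission status assessment).*

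Keep the date last seen for OS.

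The cost is one sentence, with no added visits or scans. Some PFS times become slightly shorter. A patient who stops in cycles 1-3, for whom section 9.5 requires no PET at withdrawal, and who is lost before month 3 would be censored at PET0 and contribute no PFS follow-up; the number of such patients should be reported. The protocol does not show what the follow-up forms record, so the sponsor should confirm that they capture the date of each remission assessment. The change does not recover progressions that were never looked for; it only stops that time being counted as progression-free.
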